6.3.4 Response Criteria

6.3.4.1 Evaluation of Target Lesions

Complete Response (CR): Disappearance of all target lesions. Any pathological lymph nodes (whether target or non-target) must have reduction in short axis to <10 mm.

Partial Response (PR): At least a 30% decrease in the sum of the diameters of target lesions, taking as reference the baseline sum of diameters.

Progressive Disease (PD): At least a 20% increase in the sum of the diameters of target lesions, taking as reference the smallest sum on study (this includes the baseline sum if that is the smallest on study). In addition to the relative increase of 20%, the sum must also demonstrate an absolute increase of at least 5 mm. (Note: the appearance of one or more new lesions is also considered progressions).

Stable Disease (SD): Neither sufficient shrinkage to qualify for PR nor sufficient increase to qualify for PD, taking as reference the smallest sum of diameters while on study.

6.3.4.2 Evaluation of Non-Target Lesions

Complete Response (CR): Disappearance of all non-target lesions and normalization of tumor marker level. All lymph nodes must be non-pathological in size (<10 mm short axis).

Note: If tumor markers are initially above the upper normal limit, they must normalize for a patient to be considered in complete clinical response.

Non-CR/Non-PD: Persistence of one or more non-target lesion(s) and/or maintenance of tumor marker level above the normal limits.

Progressive Disease (PD): Appearance of one or more new lesions and/or *unequivocal progression* of existing non-target lesions. *Unequivocal progression* should not normally trump

target lesion status. It must be representative of overall disease status change, not a single lesion increase.

Although a clear progression of “non-target” lesions only is exceptional, the opinion of the treating physician should prevail in such circumstances, and the progression status should be confirmed at a later time by the review panel (or Principal Investigator).

6.3.4.3 Evaluation of Best Overall Response

The best overall response is the best response recorded from the start of the treatment until disease progression/recurrence (taking as reference for progressive disease the smallest measurements recorded since the treatment started). The patient's best response assignment will depend on the achievement of both measurement and confirmation criteria.

For Patients with Measurable Disease (i.e., Target Disease)

Target Lesions	Non-Target Lesions	New Lesions	Overall Response	Best Overall Response when Confirmation is Required*
CR	CR	No	CR	≥ 4 wks. Confirmation**
CR	Non-CR/Non-PD	No	PR	≥ 4 wks. Confirmation**
CR	Not evaluated	No	PR	
PR	Non-CR/Non-PD/not evaluated	No	PR	Documented at least once ≥ 4 wks. from baseline**
SD	Non-CR/Non-PD/not evaluated	No	SD	
PD	Any	Yes or No	PD	no prior SD, PR or CR
Any	PD***	Yes or No	PD	
Any	Any	Yes	PD	

* See RECIST 1.1 manuscript for further details on what is evidence of a new lesion.

** Only for non-randomized trials with response as primary endpoint.

*** In exceptional circumstances, unequivocal progression in non-target lesions may be accepted as disease progression.

Note: Patients with a global deterioration of health status requiring discontinuation of treatment without objective evidence of disease progression at that time should be reported as “*symptomatic deterioration*.” Every effort should be made to document the objective progression even after discontinuation of treatment.

For Patients with Non-Measurable Disease (i.e., Non-Target Disease)

Non-Target Lesions	New Lesions	Overall Response
CR	No	CR
Non-CR/non-PD	No	Non-CR/non-PD*
Not all evaluated	No	not evaluated
Uequivocal PD	Yes or No	PD
Any	Yes	PD

* ‘Non-CR/non-PD’ is preferred over ‘stable disease’ for non-target disease since SD is increasingly used as an endpoint for assessment of efficacy in some trials so to assign this category when no lesions can be measured is not advised

6.3.5 Duration of Response

6.3.5.1 Duration of overall response

The duration of overall response is measured from the time measurement criteria are met for CR or PR (whichever is first recorded) until the first date that recurrent or progressive disease is objectively documented (taking as reference for progressive disease the smallest measurements recorded since the treatment started).

The duration of overall CR is measured from the time measurement criteria are first met for CR until the first date that progressive disease is objectively documented.

6.3.5.2 Duration of stable disease

Stable disease is measured from the start of the treatment until the criteria for progression are met, taking as reference the smallest measurements recorded since the treatment started, including the baseline measurements.

6.4 MODIFIED IMMUNE-RELATED RESPONSE CRITERIA (irRC)

Modified immune-related response criteria (irRC) will also be employed in this study. This new classification is based on the recent learning from clinical studies with cancer immunotherapies that even if some new lesions appear at the beginning of a treatment or if the total tumor burden does not increase substantially, tumor regressions or stabilizations might still occur later. The irRC were created using bi-dimensional measurements (as previously widely used in the World Health Organization criteria). For this trial, the concepts of the irRC are combined with RECIST 1.1 to come up with the modified irRC. Please refer to [Appendix B](#), for further details.

6.5 TOXICITY CRITERIA

The following adverse event management guidelines are intended to ensure the safety of each patient while on the study. The descriptions and grading scales found in the revised NCI

Common Terminology Criteria for Adverse Events (CTCAE) version 4.0 will be utilized for AE reporting. All appropriate treatment areas should have access to a copy of the CTCAE version 4.0. A copy of the CTCAE version 4.0 can be downloaded from the CTEP web site (http://ctep.cancer.gov/protocolDevelopment/electronic_applications/ctc.htm#ctc_40).

7 NIH REPORTING REQUIREMENTS/DATA AND SAFETY MONITORING PLAN

7.1 DEFINITIONS

Please refer to definitions provided in Policy 801: Reporting Research Events found [here](#).

7.2 OHSRP OFFICE OF COMPLIANCE AND TRAINING / IRB REPORTING

7.2.1 Expedited Reporting

Please refer to the reporting requirements in Policy 801: Reporting Research Events and Policy 802 Non-Compliance Human Subjects Research found [here](#). Note: Only IND Safety Reports that meet the definition of an unanticipated problem will need to be reported per these policies.

7.2.2 IRB Requirements for PI Reporting at Continuing Review

Please refer to the reporting requirements in Policy 801: Reporting Research Events found [here](#).

7.3 NCI CLINICAL DIRECTOR REPORTING

Problems expeditiously reported to the OHSRP in iRIS will also be reported to the NCI Clinical Director. A separate submission is not necessary as reports in iRIS will be available to the Clinical Director.

In addition to those reports, all deaths that occur within 30 days after receiving a research intervention should be reported via email to the Clinical Director unless they are due to progressive disease.

To report these deaths, please send an email describing the circumstances of the death to [name] at [contact] within one business day of learning of the death.

7.4 NIH REQUIRED DATA AND SAFETY MONITORING PLAN

The clinical research team will meet on a regular basis when patients are being actively treated on the trial to discuss each patient.

All data will be collected in a timely manner and reviewed by the principal investigator or a lead associate investigator. Events meeting requirements for expedited reporting as described in section [7.2.1](#) will be submitted within the appropriate timelines.

The principal investigator will review adverse event and response data on each patient to ensure safety and data accuracy. The principal investigator will personally conduct or supervise the investigation and provide appropriate delegation of responsibilities to other members of the research staff.

7.5 SAFETY REPORTING CRITERIA TO THE PHARMACEUTICAL COLLABORATOR (MERCK)

7.5.1 Auditing and Monitoring.

With reasonable advance notice and at reasonable times, during and after the completion of the Protocol, NCI will permit Collaborator or its designee(s) to access the NIH Clinical Center to audit the conduct of the research, as well as to audit source documents containing Raw Data, to

the extent necessary to verify compliance with FDA Good Clinical Practice (International Conference on Harmonization (ICH) E6: “Good Clinical Practice: Consolidated Guidance; 62 Federal Register 25, 691 (1997)) and the Protocol(s”).

7.5.2 Safety Reports.

The Principal Investigator will report to Merck all SAEs which involve death or a life-threatening event which are deemed to be possibly, probably, or definitely related to Pembrolizumab within two (2) calendar days of receipt of these events by the Principal Investigator.

The Principal Investigator will use its best efforts to report other SAEs whether or not related to Pembrolizumab to the Collaborator within six (6) calendar days of receipt of these events by the Principal Investigator. Adverse Event reports of cancer will be provided to Merck when the Principal Investigator receives them. The Collaborator Global Safety department will receive Adverse Experience Reports, from the Principal Investigator via [contact]) or secure email ([contact]). Data exchange of individual adverse event reports exchanged will be confirmed within one (1) business day. If confirmation is not received, then the Principal Investigator will contact Collaborator to determine if the original report needs to be re-sent.

8 STATISTICAL CONSIDERATIONS

The primary objective of this study is to determine in a preliminary, limited size trial whether Pembrolizumab in combination with CAPOX is associated with a 5-month progression free probability, which exceeds 25% when used to treat patients with biliary tract cancer.

Based on our analysis of data from previous trials of patients with similar eligibility requirements the median progression free survival in biliary tract carcinoma is 2.5 months. This translates to 25% without progressive disease at 5 months following an exponential failure model. Based on these results, it would be useful to demonstrate whether Pembrolizumab in combination with CAPOX is able to be associated with a median PFS of 5 months, which would correspond to 50% of patients having stable disease at 5 months. The trial will be conducted using a two-stage optimal design (Simon R, Controlled Clinical Trials, 10:1-10, 1989). In order to attempt to determine if the agent offers any improvement, using alpha=0.10 and beta =0.10 as acceptable error probabilities, the trial will target 50% as the desirable proportion of patients who are still without progression at the five-month evaluation ($p_1=0.50$), and will be considered inadequate if only a fraction consistent with 20% are without progression by the same evaluation time ($p_0=0.20$).

Initially, 10 patients will be enrolled and evaluated for progression. Enrollment will be temporarily halted after the 10th patient has been accrued, unless we know that 3 patients have passed the 5-month point without progression. If 3 or more of the first 10 patients enrolled have not progressed at the 5-month evaluation, then accrual will continue until a total of 17 patients have been entered. If, among the first 10 patients accrued, 0 to 2 are able to be progression-free at the 5-month evaluation, then no further patients will be enrolled after such a determination has been made. If 6 or more of the total cohort of 17 patients have been found to be progression-free at 5 months, then this will indicate an adequate progression free probability to justify further consideration of Pembrolizumab in combination with CAPOX in this population of patients. On the other hand, if 3 to 5 of 17 are progression-free at 5 months, this will be considered

insufficient. Under the null hypothesis (20% progression free at 5 months), the probability of being able to stop accrual after 10 patients have been evaluated at 5 months is 68%.

In addition to evaluation of the proportion of patients that are progression-free at 5 months, the progression-free survival for patients will also be analyzed via a Kaplan-Meier curve. This curve will be compared informally to other published results in similar patients. As well, the overall response rate will be reported, and the overall survival will be reported using a Kaplan-Meier curve. It is anticipated that up to 10 patients per year will be able to enroll onto this protocol. Thus, it is expected that accrual of up to 17 total patients can be completed in approximately 2 years. In order to allow for a small number of unevaluable patients, the accrual ceiling will be set at 19 patients.

To evaluate the response rate, proportion of patients obtaining CR and PR per RECIST 1.1 criteria of all evaluable patients will be analyzed.

To address safety, tolerability and feasibility of Pembrolizumab in combination with CAPOX chemotherapy, adverse events will be tabulated by grade according to CTCAE and analyzed and reported descriptively.

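### Section 8 aims to exceed a 25% historical rate but tests against 20% without giving a reason; at a true 25% the go/no-go rule passes the regimen 21% of the time

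*Combined protocol and SAP*

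**What the plan says.** All the relevant statements are in Section 8 (Statistical Considerations).

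- **Objective.** The trial is to determine whether the combination "is associated with a 5-month progression free probability, which exceeds 25" percent.
- **Benchmark.** The sponsor's analysis of earlier trials with similar eligibility gave a median PFS of 2.5 months. "This translates to 25% without progressive disease at 5 months following an exponential failure model".
- **Design hypotheses.** A Simon optimal two-stage design is used, "using alpha=0.10 and beta =0.10 as acceptable error probabilities". The desirable rate is p1 = 0.50. The low rate is p0 = 0.20, and the outcome "will be considered inadequate if only a fraction consistent with 20% are without progression by the same evaluation time".
- **Decision rule.** Accrual stops if 0 to 2 of the first 10 patients are progression-free at 5 months. Otherwise it continues to 17. "If 6 or more of the total cohort of 17 patients have been found to be progression-free at 5 months", the combination merits further consideration; "if 3 to 5 of 17 are progression-free at 5 months, this will be considered" insufficient.
- **Stated operating characteristic.** With 20% named as the null, the plan reports that "the probability of being able to stop accrual after 10 patients have been evaluated at 5 months is 68" percent.

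Section 1.1.1 and the Précis give the primary objective simply as determining the 5-month PFS, with no threshold. The 25% figure appears only in Section 8.

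**The concern.** The rate the trial sets out to exceed and the rate it tests against are different numbers in the same section. The 25% serves as both the objective and the historical reference. The 20% serves as p0, as the named null, and as the basis of the 68% stopping probability. Nothing in the supplied text explains the step from one to the other.

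The 6-of-17 cutoff is the only formal go/no-go criterion; the Kaplan-Meier comparison with published results is described as informal. The accepted 0.10 error applies to a regimen worse than the sponsor's historical benchmark, not to one that merely equals it. A reader who takes the objective at its word would assume that a pass shows a rate above 25% with a 10% false-positive risk. The plan gives no operating characteristic at 25% from which to judge that assumption.

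**Working it through.** **Inputs (all from Section 8):** median PFS 2.5 months under an exponential model; p0 = 0.20; p1 = 0.50; stop if 2 or fewer of 10; success if 6 or more of 17; stated alpha 0.10, beta 0.10 and early-stopping probability 68%.

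**1. The benchmark.** With exponential PFS, S(5) = 0.5^(5/median).
- Median 2.5 months: 0.5^(5/2.5) = 0.25, as stated.
- For S(5) = 0.20: median = 5 × ln(0.5)/ln(0.20) = 2.15 months. This median appears nowhere in the documents.

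**2. Formulas for the rule.** Let X be the number progression-free among the first 10 and Y the number among the next 7, both binomial with true rate p.
- P(stop after 10) = P(X ≤ 2).
- P(pass) = P(X=3)·P(Y≥3) + P(X=4)·P(Y≥2) + P(X=5)·P(Y≥1) + P(X≥6).

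**3. Reproducing the plan's figures at p = 0.20.**
- P(stop) = 0.1074 + 0.2684 + 0.3020 = 0.678, matching 68%.
- P(pass) = 0.2013×0.1480 + 0.0881×0.4233 + 0.0264×0.7903 + 0.0064 = 0.094, within 0.10.
- At p = 0.50, P(pass) = 0.1172×0.7734 + 0.2051×0.9375 + 0.2461×0.9922 + 0.3770 = 0.904, so beta is within 0.10.
- An exhaustive search for p0 = 0.20, p1 = 0.50 with both limits at 0.10 returns exactly this design as optimal.

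**4. The same rule at the benchmark, p = 0.25.**
- P(stop) = 0.0563 + 0.1877 + 0.2816 = 0.526.
- P(pass) = 0.2503×0.2436 + 0.1460×0.5551 + 0.0584×0.8665 + 0.0197 = 0.0610 + 0.0810 + 0.0506 + 0.0197 = 0.212.

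| True 5-month rate | Median PFS (exponential) | P(stop after 10) | P(declare adequate) |
|---|---|---|---|
| 20% | 2.15 months | 0.678 | 0.094 |
| 25% | 2.5 months | 0.526 | 0.212 |
| 50% | 5 months | 0.055 | 0.904 |

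**5. Where the 0.10 limit is met.** Solving P(pass) = 0.10 gives p = 0.203, a median of 5 × ln(0.5)/ln(0.203) = 2.17 months. Above that rate the error exceeds 0.10.

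**6. The smallest passing result.** 6/17 = 35%. Ignoring the interim look, P(6 or more of 17) is 0.106 at a true 20% and 0.235 at a true 25%. Since the first figure exceeds 0.10, the simple one-sided 90% exact lower limit for 6/17 lies just below 20%. It therefore does not exclude 25%.

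**The case against.** The best defence is that the design is sound for the null it names. The plan states p0 = 0.20 twice, gives the full rule, and never claims 0.10 control at 25%; anyone can work out the 25% figure from what is printed. Simon designs need only an uninteresting rate and a desirable one, and a sponsor may set the uninteresting rate below a historical estimate. The 25% is itself a point estimate of unstated precision resting on an exponential assumption. The trial is described as preliminary and small, and success leads only to further consideration, not to an efficacy claim.

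Much of this stands. There is no arithmetic error, and a false-go probability of 0.21 does not invalidate a small phase 2 trial. It does not answer the point, however. The plan itself adopts 25% as the rate to exceed and describes the design as a test of whether there is any improvement, so the error rate at 25% is the one that bears on the stated aim. Uncertainty in the benchmark could justify a lower null, but the plan does not make that argument. The preliminary setting may justify an alpha of 0.10; it does not justify leaving unstated that the risk at the benchmark is twice that.

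It can also be said that text edits disclose the 0.21 without reducing it, and that removing the threshold from the Section 8 objective softens the aim. That is true. Reducing the error means changing the cutoff or adding patients, which has its own costs and conditions.

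**Conclusion.** The concern holds. The Section 8 objective and the design null are unreconciled, and the accepted 0.10 error does not apply to the objective as written. At the plan's own historical rate, the probability of declaring the regimen adequate is 0.212 instead of at most 0.10, and the probability of stopping after 10 patients is 0.526 instead of 0.678. Error control at 0.10 extends only to a true rate of 20.3%. A result of 6 of 17 cannot be presented as showing a rate above 25% at that level.

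These figures assume 17 evaluable patients, each with a known binary 5-month status, and that the ceiling of 19 only replaces unevaluable patients. If all 19 were counted against an unchanged cutoff of 6, the pass probability at 25% would rise to 0.276. The absence of a rationale is established for the supplied text only.

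**What to change.** Make three text edits in Section 8, leaving the rule and the sample size as they are.

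1. State why p0 = 0.20 was chosen when the historical rate is 25%.
2. Add wording such as: *The rule controls type I error at 0.10 only against a 5-month rate of 20%. At a true rate of 25%, the probability of declaring the regimen adequate is 0.21 and the probability of stopping after 10 patients is 0.53. A result of 6 of 17 will not be presented as showing that the rate exceeds 25%.*
3. Align the Section 8 objective with Section 1.1.1: determine the 5-month PFS, naming 25% as the historical reference.

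The cost is the text amendment alone.

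Testing against 25% is open only if no 5-month outcomes are yet known; the trial is open-label, so a later change of cutoff would be data-dependent. Raising the cutoff to 7 of 17 gives type I error 0.103 at 25% and power 0.823 at 50%, missing both 0.10 limits. Designs that meet both are at least 3 of 10 then at least 10 of 27 (0.099, power 0.904), or at least 3 of 11 then at least 10 of 26 (0.086, power 0.901). Both exceed the ceiling of 19. They need 27 − 17 = 10 or 26 − 17 = 9 more evaluable patients, roughly another year at the anticipated 10 per year. The text edits do not depend on this choice and are the recommended course.

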3.5 STUDY CALENDAR

	Screening	Baseline	Cycles 1-6⁵	Cycle 7- to PD⁵	EOT⁹	Follow Up¹⁰
Pembrolizumab ¹			X	X		
Oxaliplatin ²			X			
Capecitabine ³			X			
Informed consent	X					
Medical history ⁴	X	X				
Concomitant meds			X	X		
Adverse event evaluation			X	X	X	
Physical exam ⁴	X	X	X	X	X	
Vital signs ⁴	X	X	X	X	X	
Height	X					
Weight ⁴	X		X	X		
Performance Status ⁴	X		X	X	X	
CBC w/differential, Platelets ⁴	X		X ¹³	X ¹³	X	
PT, INR, PTT, Fibrinogen			X ¹³	X ¹³	X	
Serum chemistry ^{4, 12}	X		X ¹³	X ¹³	X	
HIV, Hepatitis B and C serology and/or viral load	X					
HLA		X				
Thyroid Panel			X ¹³	X ¹³	X	
TB testing (if clinically indicated)	X					
Serum or urine pregnancy test ⁴	X	X				

	Screening	Baseline	Cycles 1-6 ⁵	Cycle 7- to PD ⁵	EOT ⁹	Follow Up ¹⁰
Tumor markers: aFP, CEA or Ca 19.9 ⁴			X ¹³	X ¹³		
EKG ⁴	X	X				
Confirmation of dx by NCI LP	X					
Restaging radiologic Evaluation ⁴	X	X	X ⁶	X ⁶		
Optional Tumor biopsy		X	X ⁷			
Immune monitoring ¹¹			X	X		
Blood for TCR beta sequencing ¹⁴			X	X		
Advance Directive ⁸		X				
Annual telephone contact						X

¹ 200 mg of Pembrolizumab will be administered as a 30-minute IV infusion Day 1 of each cycle.

² Oxaliplatin will be administered on D1 of each cycle at a dose of 130mg/m² IV

³ Capecitabine will be administered at a dose of 750 mg/m² PO every 12 hours. Doses will be rounded downward to the nearest 150 mg. Patients will begin Capecitabine dosing on the Day 1 of each cycle and will continue to receive Capecitabine for 14 days.

⁴ Tests performed at screening do not need to be repeated on baseline or Cycle 1 Day 1 if performed in designated time frame

⁵ Each cycle is 21 days. Trial treatment may be administered up to 3 days before or after the scheduled Day 1 of each cycle due to administrative reasons.

⁶ CT/PET/MRI of chest abdomen and pelvis. Restaging scans every 9 weeks +/- 7 days.

⁷ Performed on cycle 3 Day 1 only +/- 7 days

⁸ As indicated in section **10.3**, all subjects will be offered the opportunity to complete an NIH Advance Directive form. This should be done preferably at baseline but can be done at any time during the study as long as the capacity to do so is retained. The completion of the form is strongly recommended but is not required.

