6.3.1 Definitions

Evaluable for toxicity: All patients will be evaluable for toxicity from the time of their first treatment with pembrolizumab.

Evaluable for objective response: Only those patients who have measurable disease present at baseline, have received at least one cycle of therapy, and have had their disease re-evaluated will be considered evaluable for response. These patients will have their response classified according to the definitions stated below. (Note: Patients who exhibit objective disease progression prior to the end of cycle 1 will also be considered evaluable.)

Evaluable Non-Target Disease Response: Patients who have lesions present at baseline that are evaluable but do not meet the definitions of measurable disease, have received at least one cycle of therapy, and have had their disease re-evaluated will be considered evaluable for non-target disease. The response assessment is based on the presence, absence, or unequivocal progression of the lesions.

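### The response rate is taken over evaluable patients only, so treated patients who are never re-evaluated leave the denominator instead of counting as non-responders (minor; secondary endpoint)

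*Combined protocol and SAP*

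**What the plan says.** Response rate is a secondary objective (Section 1.1.2). Section 8 sets its analysis in one sentence: the "proportion of patients obtaining CR and PR per RECIST 1.1 criteria of all evaluable patients will be analyzed". Section 8 does not define evaluable. The definition is in Section 6.3.1, where only patients with measurable disease at baseline who "have received at least one cycle of therapy, and have had their disease re-evaluated will be considered evaluable for response" qualify. One exception follows: "Patients who exhibit objective disease progression prior to the end of cycle 1 will also be considered evaluable". Neither death nor clinical deterioration without a scan is mentioned there.

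For toxicity, the same section uses a wider set: "All patients will be evaluable for toxicity from the time of their first treatment with pembrolizumab".

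The imaging schedule in Section 3.5, footnote 6, reads "Restaging scans every 9 weeks +/- 7 days", and Section 6.3 gives the same 9-week interval. A cycle lasts 3 weeks (Section 3.2). The documents contain no response analysis over all treated patients.

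**The concern.** A patient who has been treated but never re-evaluated has no recorded response. The usual convention in a single-arm trial is to keep that patient in the denominator as a non-responder. Under Sections 8 and 6.3.1 read together, the patient disappears from the calculation unless objective progression was shown before the end of cycle 1.

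The schedule leaves room for this. Cycle 1 ends at week 3 and the first planned scan is at week 9, with a window from week 8 to week 10. A patient who completes cycle 1 and then dies or stops in the following weeks without an unscheduled scan meets neither the definition nor its exception.

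Such patients cannot have been recorded as responders, so leaving them out works in one direction only. What is at stake is how the reported rate reads beside other small trials in this disease. No decision in this trial depends on it.

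**Working it through.** **Inputs from the documents.** Stage 1 has 10 patients, the full cohort 17, and the accrual ceiling is 19 (Section 8). Section 8 gives no target, precision or decision rule for the response rate, so there is no planned response figure to reproduce. The one design figure used here is the stated 68% chance of stopping after 10 patients if the true 5-month rate is 20%. It reproduces: P(X ≤ 2 | n = 10, p = 0.20) = 0.1074 + 0.2684 + 0.3020 = 0.678. A final sample of about 10 is therefore a realistic case.

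**Assumed inputs.** Let x be the number of responders and k the number of treated patients with no re-evaluation and no objective progression in cycle 1. The documents give neither. The nearest hint for k is "In order to allow for a small number of unevaluable patients, the accrual ceiling will be set at 19 patients", which allows 19 - 17 = 2 patients, or 2/19 = 10.5%. It is not specific to response. The same share of 10 patients is about 1. I therefore take k = 1 to 2 at N = 17 or 19, and k = 1 at N = 10.

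**Who leaves the denominator.**

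- Objective progression before the end of cycle 1: stays in, through the exception.
- At least one cycle and any later re-evaluation, scheduled or not: stays in.
- No re-evaluation and no objective progression in cycle 1: leaves.
- Less than one cycle, no objective progression in cycle 1, scanned later: leaves too, but may be a responder.
- No measurable disease at baseline: should not occur, because inclusion criterion 2.1.1.3 requires it.

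**Size for patients never re-evaluated.** The all-treated rate is x/N and the planned rate is x/(N - k). Their ratio is N/(N - k), whatever x is (x > 0).

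| N | k | N/(N - k) |
|---|---|---|
| 19 | 1 | 19/18 = 1.06 |
| 19 | 2 | 19/17 = 1.12 |
| 17 | 1 | 17/16 = 1.06 |
| 17 | 2 | 17/15 = 1.13 |
| 10 | 1 | 10/9 = 1.11 |

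**Against sampling error.** The exact (Clopper-Pearson) 95% limits for x of n are the 0.025 quantile of Beta(x, n - x + 1) and the 0.975 quantile of Beta(x + 1, n - x). With x = 3 assumed:

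- all treated, 3/19 = 15.8% (3.4% to 39.6%)
- k = 1, 3/18 = 16.7% (3.6% to 41.4%)
- k = 2, 3/17 = 17.6% (3.8% to 43.4%)

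The largest shift is 17.6 - 15.8 = 1.8 percentage points, against an interval 39.6 - 3.4 = 36.2 points wide. At N = 10 with x = 2 assumed, 2/10 = 20.0% (2.5% to 55.6%) becomes 2/9 = 22.2% for k = 1, a shift of 2.2 points against a width of 53.1.

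**Patients with under one cycle who are scanned later.** Here the formula does not apply, because a responder would leave the numerator as well. If one of the 3 responders in 19 were such a patient, the planned rate would be 2/18 = 11.1%, below 15.8%. If the patient were a non-responder, it would be 3/18 = 16.7%. The direction is not fixed.

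**The case against.** The best defence is that the rule is fixed in advance and openly defined, the endpoint is secondary and descriptive, and a report giving treated and evaluable counts for at most 19 patients lets any reader recompute the rate. Early deaths still appear in the overall survival curve. Section 6.3.4.3 also asks for efforts to document progression after treatment stops, which should keep k low. All of this stands, and it limits the point to a minor one. It does not remove it: a wide interval describes sampling error and does not correct a one-sided choice of denominator.

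Four stronger readings are tempting, and the documents do not support them.

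- A reader might infer from the symptomatic-deterioration note in Section 6.3.4.3 that the protocol expects patients with no re-evaluation. That note concerns "Patients with a global deterioration of health status requiring discontinuation of treatment without objective evidence of disease progression at that time". A patient stable at week 9 who deteriorates later fits it, is evaluable, and already counts as a non-responder.
- A reader might take the exponential model in Section 8 (median 2.5 months), under which about 44% have progressed or died by week 9, as the share excluded. Only those never re-evaluated are excluded, and their share is not given.
- A reader might use larger values, such as 3 of 10 patients lost. That is 30%, well above the allowance of 2 in 19.
- A reader might infer that early failures can be replaced as unevaluable in the primary analysis, raising its error rate. Section 8 states no replacement rule, and its success criterion refers to a fixed cohort: "If 6 or more of the total cohort of 17 patients have been found to be progression-free at 5 months". Read literally, early failures stay in that count.

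**Conclusion.** The point holds as a minor one. As written, the plan removes treated patients with no re-evaluation from the response denominator, and for these patients the reported rate can only be raised or left unchanged. The factor is 1.06 to 1.12 for one or two such patients among 19, and 1.11 for one among 10. It is 1 if every treated patient is re-evaluated. These sizes rest on assumed values of k, guided only by the general allowance of two unevaluable patients. The one-directional claim does not extend to patients with less than one cycle who are scanned later. The stage-1 and final rules, the sample size and the error rates for 5-month progression-free status do not use this denominator and are unaffected.

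**What to change.** In Section 8, define the response rate as confirmed or recorded CR plus PR, on whatever basis the plan already uses, divided by all treated patients. This is the set that Section 6.3.1 already uses for toxicity. State that patients without a post-baseline assessment count as non-responders, report an exact 95% confidence interval, and keep the rate in the evaluable set as a sensitivity analysis. Patients with less than one cycle who are scanned later would then be counted by their observed response.

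This takes a sentence or two. It needs no new data or visits and changes neither the sample size nor the decision rule. The only downside is a slightly lower reported rate if any treated patient is never re-evaluated.
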